**Figure 5.5-2: Simulated nivolumab exposure for a single dose of 480 mg and 960 mg**

The solid lines and shaded band represent the simulation-based median and 90% prediction intervals. The dotted lines and values represent median and 95th percentile.

Analysis directory source: /global/pkms/data/CA/209/923/prd/ppk/final  
PPK model: Analysis directory/nm/a-2202-3p1.ctf

**Table 5.5-1: Comparisons of  $C_{min}$ ,  $C_{max}$ , and  $C_{avg}$  for geometric mean and median of 3mg/kg Q2W steady state and 480 mg and 960 mg single dosing regimens**

Summary Exposure	3 mg/kg Q2W Steady State GM [ $\mu\text{g/mL}$ ] (%CV)	480 mg Single Dose GM [ $\mu\text{g/mL}$ ] (%CV)	% Difference in GMs	3 mg/kg Q2W Steady State Median [ $\mu\text{g/mL}$ ] (5th, 95th percentile)	480 mg Single Dose Median [ $\mu\text{g/mL}$ ] (5th, 95th percentile)
$C_{min}$	63.9 ( 62.5 )	21.6 ( 39 )	-66.2	66.4 ( 27.9 , 120 )	22.3 ( 10.6 , 39.3 )
$C_{max}$	126 ( 51.2 )	123 ( 85.4 )	-2.38	126 ( 74.9 , 202 )	121 ( 74.7 , 204 )
$C_{avg}$	83.5 ( 51.3 )	42.7 ( 28.5 )	-48.9	85.1 ( 42.7 , 143 )	42.8 ( 27 , 67.7 )

Summary Exposure	3 mg/kg Q2W Steady State GM [ $\mu\text{g/mL}$ ] (%CV)	960 mg Single Dose GM [ $\mu\text{g/mL}$ ] (%CV)	% Difference in GMs	3 mg/kg Q2W Steady State Median [ $\mu\text{g/mL}$ ] (5th, 95th percentile)	960 mg Single Dose Median [ $\mu\text{g/mL}$ ] (5th, 95th percentile)
$C_{min}$	63.9 ( 62.5 )	43.2 ( 39 )	-32.4	66.4 ( 27.9 , 120 )	44.6 ( 21.2 , 78.6 )
$C_{max}$	126 ( 51.2 )	246 ( 85.4 )	95.2	126 ( 74.9 , 202 )	242 ( 149 , 408 )
$C_{avg}$	83.5 ( 51.3 )	85.4 ( 28.5 )	2.28	85.1 ( 42.7 , 143 )	85.6 ( 54 , 135 )

$C_{min}$ : Trough nivolumab serum concentration,  $C_{max}$ : Peak nivolumab serum concentration,  $C_{avg}$ : Average nivolumab serum concentration, GM: Geometric mean, CV: Coefficient of variation

Analysis directory source: /global/pkms/data/CA/209/923/prd/ppk/final  
PPK model: Analysis directory/nm/a-2202-3p1.ctf

## 6. STUDY POPULATION

For entry into the study, the following criteria MUST be met.

### 6.1 Inclusion Criteria

#### 1) Signed Written Informed Consent

- a) The informed consent form signed by the participant or the participant's legally acceptable representative

#### 2) Type of Participant and Target Disease Characteristics

- a) Men and women ages  $\geq 18$  years old
- b) Participant has documented OR suspected infection
  - i) Documented infection is infection confirmed with a microbiologic diagnosis
  - ii) Suspected infection is infection being treated with ongoing antimicrobial therapy at the time of study treatment administration
- c) Participant has the onset of severe sepsis or septic shock at least 24 hours prior to study treatment administration based on having at least 1 of the 3 organ dysfunction criteria below. Organ dysfunction must be new and thought to be due to sepsis.
  - i) Hypotension defined as the need for treatment with any vasopressor(s) for at least 6 hours to maintain a systolic pressure  $\geq 90$  mmHg or a mean arterial pressure  $\geq 70$  mmHg  
OR
  - ii) Acute respiratory failure defined as the need for invasive mechanical ventilation for at least 24 hours to support pulmonary function  
OR
  - iii) Acute kidney injury defined as creatinine  $> 2.0$  mg/dL (from a creatinine that was within the normal reference range prior to onset of sepsis) OR urine output  $< 0.5$  mL/kg/hr for  $> 2$  hours despite adequate fluid resuscitation. In the presence of pre-existing impairment of renal function (defined as a serum creatinine concentration  $> 2$  times the upper limit of the normal reference range prior to the onset of sepsis), the participant should meet 1 of the other 2 organ dysfunction criteria above.
- d) Participant has sepsis-associated immunosuppression based on an absolute lymphocyte count  $\leq 1100$  cells/ $\mu$ L on at least one assessment within the 96 hours prior to study treatment administration
- e) Participant is in an intensive care unit at the time of study treatment administration and, based on their medical condition, there are no plans to discharge from the ICU in the next 24 hours
- f) Participant Re-enrollment: This study permits the re-enrollment of a participant who has discontinued the study as a pre-treatment failure (ie, participant has not been randomized /has not been treated). If re-enrolled, the participant must be re-consented.

### 3) Age and Reproductive Status

- a) Women of childbearing potential (WOCBP) must have a negative serum or urine pregnancy test (minimum sensitivity 25 IU/L or equivalent units of HCG) within 24 hours prior to the start of study treatment
- b) Women must not be breastfeeding
- c) Women of childbearing potential (WOCBP) must agree to follow instructions for method(s) of contraception for the duration of treatment with nivolumab plus 5 half-lives of nivolumab (the terminal half-life of nivolumab is up to 25 days) plus 30 days (duration of ovulatory cycle) for a total of 5 months post-treatment completion (See [Appendix 4](#)).
- d) Males who are sexually active with WOCBP must agree to follow instructions for method(s) of contraception ([Appendix 4](#)) for the duration of treatment with nivolumab plus 5 half-lives of nivolumab plus 90 days (duration of sperm turnover) for a total of 7 months post-treatment completion. In addition, male participants must be willing to refrain from sperm donation during this time (See [Appendix 4](#)).
- e) Azoospermic males are exempt from contraceptive requirements.
- f) WOCBP who are continuously not heterosexually active are also exempt from contraceptive requirements but still must undergo pregnancy testing as described in this section.

Investigators shall counsel WOCBP, and male participants who are sexually active with WOCBP, on the importance of pregnancy prevention and the implications of an unexpected pregnancy. Investigators shall advise on the use of highly effective methods of contraception ([Appendix 4](#)) which have a failure rate of < 1% when used consistently and correctly.

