The single-dose and multiple dose pharmacokinetics of nivolumab were previously well-characterized in oncology subjects and are known to be linear and dose-proportional in the range of 0.1 to 10 mg/kg. The geometric mean (% CV) clearance (CL) was 9.5 mL/h (49.7%), geometric mean volume of distribution at steady state (Vss) was 8.0 L (30.4%), and geometric mean elimination half-life (t1/2) was 26.7 days (101%). Nivolumab accumulation following every 2 weeks administration in oncology subjects was in the range of 2.9 to 3.3 based on AUC(TAU), 2.0 to 2.4 based on Cmax, and 3.1 to 4.8 based on Cmin. There was no dose-related trend in the accumulation index of AUC(TAU), Cmax, or Cmin. There was no meaningful change in cytokines known to have indirect effects on CYP enzymes across all studied dose levels of nivolumab (0.3, 2 and 10 mg/kg) during the course of treatment. This lack of cytokine modulation suggests that nivolumab has no or low potential for modulating CYP enzymes, thereby indicating a low risk of therapeutic protein-drug interaction. Nivolumab is an IgG4 monoclonal antibody, which is likely eliminated by mechanisms similar to that of other antibodies, namely by non-specific catabolism (mainly by enzymes in the reticuloendothelial system). These enzymes are not known to be inhibited or induced by drugs, and therefore it is unlikely that other drugs will have an impact on the PK of nivolumab. The immunogenic potential of nivolumab was minimal with low titers, low persistent positive rates, low incidences of neutralizing antibodies and no impact of immunogenicity on safety or PK.

A detailed description of the chemistry, pharmacology, efficacy, and safety of nivolumab is provided in the Investigator Brochure.

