### **9.2.6 Pregnancy**

If, following initiation of the study treatment, it is subsequently discovered that a participant is pregnant or may have been pregnant at the time of study exposure, including during at least 5 half-lives after product administration, the investigator must immediately notify the BMS Medical Monitor/designee of this event and complete and forward a Pregnancy Surveillance Form to BMS Designee within 24 hours of awareness of the event and in accordance with SAE reporting procedures described in [Appendix 3](#).

In most cases, the study treatment will be permanently discontinued in an appropriate manner (e.g., dose tapering if necessary for participant safety). Please call the BMS Medical Monitor within 24 hours of awareness of the pregnancy.

Protocol-required procedures for study discontinuation and follow-up must be performed on the participant.

Follow-up information regarding the course of the pregnancy, including perinatal and neonatal outcome and, where applicable, offspring information must be reported on the Pregnancy Surveillance Form.

Any pregnancy that occurs in a female partner of a male study participant should be reported to Sponsor or designee. In order for Sponsor or designee to collect any pregnancy surveillance information from the female partner, the female partner must sign an informed consent form for disclosure of this information. Information on this pregnancy will be collected on the Pregnancy Surveillance Form.

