### **CONTRACEPTION GUIDANCE FOR FEMALE PARTICIPANTS OF CHILD BEARING POTENTIAL**

One of the highly effective methods of contraception listed below is required during study duration and until the end of relevant systemic exposure, defined as 4 months after the end of study treatment, plus 30 days (a total of 5 months).

Local laws and regulations may require use of alternative and/or additional contraception methods.

Highly Effective Contraceptive Methods That Are User Dependent
 
Failure rate of <1% per year when used consistently and correctly.a

 
• Combined (estrogen- and progestogen-containing) hormonal contraception associated with inhibition of ovulationb 
 
– oral
 
– intravaginal
 
– transdermal
 
 
 

 
• Progestogen-only hormonal contraception associated with inhibition of ovulationb 
 
– oral
 
– injectable
 
 
 

Highly Effective Methods That Are User Independent

 
• Implantable progestogen-only hormonal contraception associated with inhibition of ovulationb
 
• Intrauterine device (IUD)c
 
• Intrauterine hormone-releasing system (IUS)c
 
• Bilateral tubal occlusion
 

 
• Vasectomized partner
 
 
A vasectomized partner is a highly effective contraception method provided that the partner is the sole male sexual partner of the WOCBP and the absence of sperm has been confirmed. If not, an additional highly effective method of contraception should be used.

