**CONTRACEPTION GUIDANCE FOR MALE PARTICIPANTS WITH PARTNER(S) OF CHILD BEARING POTENTIAL.**

Male participants with female partners of childbearing potential are eligible to participate if they agree to the following during the treatment and until the end of relevant systemic exposure.

- Inform any and all partner(s) of their participation in a clinical drug study and the need to comply with contraception instructions as directed by the investigator.
- Male participants are required to use a condom for study duration and until the end of relevant systemic exposure defined as 7 months after the end of treatment in the male participant.
- Female partners of males participating in the study should consider use of effective methods of contraception until the end of relevant systemic exposure, defined as 5 months after the end of treatment in the male participant.
- Male participants with a pregnant or breastfeeding partner must agree to remain abstinent from penile vaginal intercourse or use a male condom during each episode of penile penetration during the treatment and until 5 months after the end of treatment.

- Refrain from donating sperm for the duration of the study treatment and for 7 months after the end of treatment.

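### Inclusion 3c gives 25 days as an upper limit for nivolumab half-life, below the 26.7-day geometric mean in Section 3.2; depending on the half-life used, the contraception windows miss the protocol's own rule by 0 to about 11 days

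*Protocol*

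**What the plan says.** Protocol Section 6.1, criterion 3c, requires women of childbearing potential to use contraception for the treatment period and five half-lives of nivolumab, "plus 30 days (duration of ovulatory cycle) for a total of 5 months post-treatment completion". In parentheses it gives the input: "the terminal half-life of nivolumab is up to 25 days". Criterion 3d sets the corresponding period for men: "plus 5 half-lives of nivolumab plus 90 days (duration of sperm turnover) for a total of 7 months post-treatment completion". Appendix 4 repeats the 5- and 7-month totals.

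Section 3.2 summarises the pharmacokinetics in oncology subjects: geometric mean clearance 9.5 mL/h (CV 49.7%), volume of distribution at steady state 8.0 L (CV 30.4%), and elimination half-life 26.7 days (CV 101%). Nothing in the protocol or SAP reconciles 26.7 days with a ceiling of 25 days.

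**The concern.** The 25-day figure is the input to an instruction that participants must accept in order to enter the study. It is worded as the most the half-life can be, yet it lies below the average that the protocol itself reports, in a quantity with very wide variation between subjects. If 26.7 days is the better input, the stated totals no longer deliver the protocol's own margin of five half-lives plus one ovulatory cycle or one sperm turnover. At stake is the length of that margin and the agreement between two sections of the protocol.

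**Working it through.** **Inputs.** Half-life 25 days (criterion 3c) or 26.7 days (Section 3.2). Add-on 30 days (3c) or 90 days (3d). Stated windows 5 and 7 months. The documents do not define a month; I take 365.25/12 = 30.44 days, so 5 months = 152.2 days and 7 months = 213.1 days. This is an assumption, varied below.

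**Reproducing the plan's figures.** The rule is 5 × half-life + add-on. At 25 days:
- women: 5 × 25 + 30 = 155 days, and 155/30.44 = 5.09 months
- men: 5 × 25 + 90 = 215 days, and 215/30.44 = 7.06 months

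These give 5 and 7 to the nearest whole month, so the stated totals follow from the stated input.

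**A third value from Section 3.2.** Clearance and volume imply ln 2 × 8000 mL / (9.5 mL/h × 24 h) = 24.3 days. This is also a central value. It is not strictly a terminal half-life for the two-compartment model described in Section 5.5.

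**Shortfall by half-life used (30.44-day month).**

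| Half-life | Rule, women | Short of 152.2 | Rule, men | Short of 213.1 |
|---|---|---|---|---|
| 24.3 d | 151.5 d | none | 211.5 d | none |
| 25 d | 155 d | 2.8 d | 215 d | 1.9 d |
| 26.7 d | 163.5 d | 11.3 d | 223.5 d | 10.4 d |

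Of the shortfall at 26.7 days, 5 × (26.7 − 25) = 8.5 days come from the half-life and the rest from rounding to whole months. The longest half-life the windows cover is (152.2 − 30)/5 = 24.4 days for women and (213.1 − 90)/5 = 24.6 days for men.

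**Sensitivity to the month.** Five calendar months are 150 to 153 days and seven are 212 to 215 days. At 26.7 days the shortfall is then 10.5 to 13.5 days (women) and 8.5 to 11.5 days (men). At 24.3 days the shortest calendar span would leave women 151.5 − 150 = 1.5 days short and men none.

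**What is lost at 26.7 days.** Five half-lives take 5 × 26.7 = 133.5 days, which both windows exceed. The add-on that remains is 152.2 − 133.5 = 18.7 of 30 days and 213.1 − 133.5 = 79.6 of 90 days. By simple first-order decay the drug remaining is 2^−(152.2/26.7) = 1.9% at 5 months and 2^−(213.1/26.7) = 0.4% at 7 months, against 2^−5 = 3.1% at five half-lives.

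**The case against.** The strongest reply is that the windows are not shown to be wrong. The 5- and 7-month totals follow from 25 days by ordinary rounding, and they meet the rule at the 24.3 days derived from Section 3.2. The 26.7 days come from oncology subjects. Section 3.2 does not say which dosing period they describe, while the population model in Section 5.5 has time-varying clearance. The half-life in sepsis is unknown and is an endpoint of this trial. All of this stands, and it is why the shortfall is a range that starts at zero. It does not rescue the upper-limit wording: 24.3 and 26.7 days are both central values, and neither supports a ceiling of 25.

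A second reply is that the remedy replaces one central value with another. That is fair. No bound is available in the documents, so the value should be labelled as a geometric mean and not presented as a maximum.

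A reader might also infer three stronger points that the documents do not support:
- **Appendix 4 ends exposure too early.** For women, the end of relevant systemic exposure is "defined as 4 months after the end of study treatment, plus 30 days (a total of 5 months"). Four months alone (about 122 days) would be less than five half-lives at 25 days (125). But the definition can run through the whole phrase, add-on included. The text for men supports that reading, since condom use is required "until the end of relevant systemic exposure defined as 7 months after the end of treatment in the male participant".
- **Rounding is a separate error.** Rounding to the nearest month is a convention, and here it costs 2 to 3 days.
- **Pregnancy reporting is compromised.** Section 9.2.6 covers pregnancies "including during at least 5 half-lives after product administration" without giving days. That is a minimum, and nothing suggests sites would stop reporting at a particular day because of it.

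**Conclusion.** The two half-life statements conflict, and the one in criterion 3c is wrong as an upper limit; that part is certain from the text. The consequence is conditional. With a 30.44-day month, the windows fall short of the protocol's rule by 0 to about 11 days for women and 0 to about 10 days for men, as the half-life runs from 24.3 to 26.7 days. It would be tempting to report the windows as simply 11 and 10 days too short, but that requires 26.7 days to be the right input, which the documents do not establish. Nor is there a case for a material safety gap: at 26.7 days five half-lives are still covered, and only part of the add-on is lost. No efficacy, pharmacokinetic or safety analysis depends on the figure. Severity is minor.

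**What to change.** In criterion 3c, delete the upper-limit wording and give the Section 3.2 value: about 27 days, geometric mean in oncology subjects. Re-derive the windows from 26.7 days and round up, to at least 164 days for women and 224 days for men. Windows of 24 and 32 weeks (168 and 224 days) do this. Carry the totals into 3c, 3d and Appendix 4 so that all three agree.

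The cost is a protocol amendment with IRB/IEC approval (Appendix 2), which can be bundled with the next one. Affected participants would use contraception for about 11 to 16 days longer (224 − 213.1 = 10.9 days for men; 168 − 152.2 = 15.8 days for women). No new procedures or participants are needed.

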## 6.2 Exclusion Criteria

### 1) Medical Conditions

- a) Previous episode of severe sepsis or septic shock with ICU admission during the current hospitalization
- b) Active, known, or suspected autoimmune disease **NOTE:** Participants with type I diabetes mellitus, hypothyroidism only requiring hormone replacement, skin disorders (such as vitiligo, psoriasis, or alopecia) not requiring systemic treatment, or conditions not expected to recur in the absence of an external trigger are permitted to enroll.
- c) History of solid organ or bone marrow transplant.
- d) Known history of malignancy and has undergone treatment for such within 6 weeks prior to study treatment administration.
- e) Known history of infection with HIV and not on antiretroviral therapy prior to the current hospitalization or  $CD4 \leq 200$  cells/mm^3 or AIDS-defining illness in the past year.
- f) Known history of chronic HBV infection and not on treatment with an HBV nucleos(t)ide analogue prior to the current hospitalization or HBV DNA > 100 IU/mL.
- g) Known history of infection with HCV and currently undergoing treatment for HCV infection or has detectable HCV RNA.

- h) Known active illicit drug use disorder (defined as illicit drug use on 5 or more days in the past 30 days) OR known active alcohol use disorder (defined as drinking 5 or more alcoholic drinks on the same occasion on 5 or more days in the past 30 days)
- i) Any other sound medical, psychiatric and/or social reason as determined by the investigator

## **2) Prior/Concomitant Therapy**

- a) Prior exposure to nivolumab or to an anti-PD-1, anti-PD-L1, anti-PD-L2, anti-CD137, anti-CTLA-4 antibody, or any other antibody or drug specifically targeting T-cell co-stimulation or checkpoint pathways
- b) Prior exposure to any other investigational agent within 4 weeks or 5 half-lives (whichever is longer) of study treatment administration
- c) Prior exposure to GM-CSF (Granulocyte-macrophage colony-stimulating factor; Sargramostim; Leukine) within 4 weeks or 5 half-lives (whichever is longer) of study treatment administration

## **3) Physical and Laboratory Test Findings**

- a) Body weight  $\leq 50$  kg or  $\geq 180$  kg

## **4) Allergies and Adverse Drug Reaction**

- a) History of severe hypersensitivity reaction to monoclonal antibodies or related compounds.

## **5) Other Exclusion Criteria**

- a) Prisoners or participants who are involuntarily incarcerated. (Note: under certain specific circumstances a person who has been imprisoned may be included or permitted to continue as a participant. Strict conditions apply and Bristol-Myers Squibb approval is required.)
- b) Participants who are compulsorily detained for treatment of either a psychiatric or physical illness
- c) Concurrent participation in another interventional clinical trial of an investigational drug
- d) Presence of an advanced directive to withhold or withdraw life-sustaining treatment, a do not resuscitate (DNR) order, a no CPR order, or a comfort measures only (CMO) order
- e) Participant's family, treating physician, or both are not in favor of aggressive support of the participant

Eligibility criteria for this study have been carefully considered to ensure the safety of the study participants and that the results of the study can be used. It is imperative that participants fully meet all eligibility criteria.

## **6.3 Lifestyle Restrictions**

### **6.3.1 Meals and Dietary Restrictions**

Not applicable.

### **6.3.2 Caffeine, Alcohol and Tobacco**

Not applicable.

### **6.3.3 Activity**

Not applicable.

## **6.4 Screen Failures**

Screen failures are defined as participants who consent to participate in the clinical study but are not subsequently randomized. A minimal set of screen failure information is required to ensure transparent reporting of screen failure participants, to meet the Consolidated Standards of Reporting Trials (CONSORT) publishing requirements, and to respond to queries from regulatory authorities. Minimal information includes date of consent, demography, screen failure details, eligibility criteria, and any serious AEs.

### **6.4.1 Retesting During Screening or Lead-In Period**

**Participant Re-enrollment:** This study permits the re-enrollment of a participant that has discontinued the study as a pre-treatment failure (i.e., participant has not been randomized / has not been treated). If re-enrolled, the participant must be re-consented.

Retesting of laboratory parameters and/or other assessments within any single Screening or Lead-in period will be permitted (in addition to any parameters that require a confirmatory value).

The most current result prior to Randomization is the value by which study inclusion will be assessed, as it represents the participant's most current, clinical state.

Laboratory parameters and/or assessments that are included in [Table 2.-1 Screening Procedural Outline](#) may be repeated in an effort to find all possible well-qualified participants. Consultation with the Medical Monitor may be needed to identify whether repeat testing of any particular parameter is clinically relevant.

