## 2. SCHEDULE OF ACTIVITIES

**Table 2.-1: Screening Procedural Outline (CA209923)**

Procedure	Screening a Visit	Baseline b Visit	Notes
Eligibility Assessments			
Informed Consent	X		A participant is considered enrolled only when a protocol specific informed consent is signed. Participants unable to give their written consent may only be enrolled in the study with the consent of a legally acceptable representative. The participant must also be informed about the nature of the study to the extent compatible with his or her understanding, and should this participant become capable, he or she should personally sign and date the consent form as soon as possible.
Inclusion/Exclusion Criteria	X	X	
Medical History	X		Include any toxicities or allergy related to previous treatments. Include any chronic medical conditions (for example, hypertension, diabetes) and past surgeries.
Safety Assessments			
Physical Examination (PE)	X	X	If the screening PE is performed within 24 hours prior to dosing on Day 1 then a single exam may count as both the screening and predose evaluation.
Physical Measurements	X		Includes height, weight, and BMI.
Vital Signs	X	X	Includes body temperature, respiratory rate, blood pressure and heart rate. Blood pressure and heart rate should be measured after the participant has been resting quietly for at least 5 minutes.
Electrocardiogram (ECGs)	X	X	ECGs should be recorded after the participant has been supine for at least 5 minutes.
Laboratory Tests			
Clinical safety laboratory tests	X	X	Includes blood and urine samples. See Section 9.4.4
Pregnancy Test	X	X	WOCBP only. See note in Section 9.4.4

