**9.4.4 Clinical Safety Laboratory Assessments**

Local laboratories will perform the analyses below and will provide reference ranges for these tests. Investigators must document their review of each laboratory safety report. Results of clinical laboratory tests performed at Screening/Baseline must be available prior to dosing.

Hematology	
Hemoglobin	
Hematocrit	
WBC count with differential to calculate absolute lymphocyte count	
Platelet count	
CD4+, CD8+ T-cell count and CD4+/CD8+ ratio	
Serum Chemistry	
Sodium	Total Protein
Potassium	Albumin
Chloride	Calcium
Bicarbonate	Phosphorus
Blood Urea Nitrogen (BUN)	Magnesium
Creatinine	Amylase
Glucose	Lipase
Aspartate aminotransferase (AST)	
Alanine aminotransferase (ALT)	
Total bilirubin [reflex to direct Bilirubin if total bilirubin is > ULN]	
Alkaline phosphatase	
Lactate dehydrogenase (LDH)	
Urinalysis	
Protein	
Glucose	

Blood
Leukocyte esterase
Specific gravity
pH
Microscopic examination of the sediment if blood, protein or leukocytes esterase are positive on the dipstick
Other Analyses
Pregnancy test for WOCBP only: at screening; within 24 hours prior to the start of study drug (an extension up to 72 hours prior to start of study drug is permissible in situations where results cannot be obtained within the standard 24 hour window); monthly until Study Discharge; whenever pregnancy is suspected.
Follicle stimulating hormone (FSH) for women only: at screening, refer to Appendix 4 for applicability.
Thyroid function testing (TSH with reflex to free T3 and free T4): at baseline; at Day 56, at index hospitalization discharge and at study discharge.

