7.2 Study Conduct

Relevant protocol deviations are summarized by treatment and total for treated subjects. Relevant protocol deviations are those that are programmable and could potentially affect the interpretability of the study results, such as:¹

- Certain inclusion or exclusion criteria;
- Incorrect dosing or study treatment assignment;

- Use of prohibited concomitant medications;
- Subjects remaining on treatment/in the study despite having met specified criteria for withdrawal.

A subject is considered to have a deviation of an inclusion or exclusion criterion only if all pre-treatment measurements fail the criterion. The consent date defines the beginning of enrollment. [Appendix 1](#) describes the relevant protocol deviations that can be programmed from the database.

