APPENDIX 1 RELEVANT PROTOCOL DEVIATIONS

The relevant protocol deviations that can be programmed from the database are identified below.

The list would be updated as appropriate if, in the course of monitoring the study, additional protocol deviations are found and considered relevant.

- Age < 18 years;
- Patient does not have documented or suspected infection prior to study drug administration;
- Patient does not have at least 1 new organ dysfunction prior to study drug administration;
- Patient does not have absolute lymphocyte (ALC) values </= 1100 cells/uL prior to study drug administration;
- Patient is not in ICU at time of study drug administration;
- Medical history of autoimmune disease;
- Medical history of bone marrow or solid organ transplant;
- Body Weight \leq 50 kg or \geq 180 kg;
- Exposure to nivolumab or to an anti-PD-1, anti-PD-L1, anti-PD-L2, anti-CD137, anti-CTLA-4 antibody, or any other antibody or drug specifically targeting T-cell co-stimulation or checkpoint pathways (#);
- Exposure to GM-CSF (Granulocyte-macrophage colony-stimulating factor; Sargramostim; Leukine) within 4 weeks or 5 half-lives (whichever is longer) of study treatment administration;
- Incorrect dosing or study treatment assignment.

Non-study medications marked above with # are identified by a BMS physician prior to database lock.

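### Criterion 2d and Section 6.4.1 give opposite entry decisions when a low lymphocyte count has recovered, and the SAP deviation check omits the 96-hour window

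*Protocol*

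**What the plan says.** Protocol Section 6.1, criterion 2d, requires an ALC of 1100 cells/µL or less "on at least one assessment within the 96 hours prior to study treatment administration". Any one value in the window is enough, and the window is counted back from dosing.

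Protocol Section 6.4.1 allows retests: "Retesting of laboratory parameters and/or other assessments within any single Screening or Lead-in period will be permitted". It then says "The most current result prior to Randomization is the value by which study inclusion will be assessed", on the ground that this value best reflects the participant's present condition. ALC is within its scope. Section 9.4.4 lists "WBC count with differential to calculate absolute lymphocyte count", and Table 2.-1 schedules "Clinical safety laboratory tests" at both screening and baseline. No sentence exempts 2d or says which passage prevails.

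SAP Section 7.2 sets the deviation rule: "A subject is considered to have a deviation of an inclusion or exclusion criterion only if all pre-treatment measurements fail the criterion". Appendix 1 words the ALC check as "Patient does not have absolute lymphocyte (ALC) values </= 1100 cells/uL prior to study drug administration", with no time limit. SAP Section 6.1 starts the pre-treatment period at screening, which Table 2.-1 allows up to 10 days before dosing.

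**The concern.** Two passages of the protocol decide entry from the same laboratory test by different rules. Where an early low count has recovered, one admits the participant and the other does not. Two sites could each follow the protocol and reach opposite decisions on the same patient.

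The SAP check is a separate matter. It shares the any-value logic of 2d but not its window, so it can pass a participant who breached 2d.

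Depressed ALC is the marker of immunosuppression used at entry, and Protocol Section 3.3 gives it as one of two entry conditions meant to avoid the early pro-inflammatory phase. At stake are consistent enrolment across sites, a correct count of relevant protocol deviations, and whether the results can be said to describe patients whose ALC was low at dosing.

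**Working it through.** The plan gives no figure on this point, so the check is mainly a comparison of the rules.

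**Step 1. The rules side by side**

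| Source | Which value counts | Window | Time anchor | Purpose |
|---|---|---|---|---|
| Protocol 6.1, 2d | any | 96 h | dosing | entry |
| Protocol 6.4.1 | latest | none stated | randomization | entry |
| SAP 7.2 and Appendix 1 | any | whole pre-treatment period | dosing | deviation report |

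Screening of up to 10 days is 10 × 24 = 240 h. The SAP check therefore accepts low values from up to 240 − 96 = 144 h that 2d does not. The protocol anchors also differ, because Table 2.-1 allows randomization on Day -1 or Day 1.

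**Step 2. Constructed sequences**

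Times are before dosing. The last value is also taken as the latest before randomization.

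| Case | ALC values (cells/µL) | 2d | 6.4.1 | SAP check |
|---|---|---|---|---|
| A | 900 at 72 h, 1400 at 12 h | eligible | not eligible | no deviation |
| B | 900 at 168 h, 1300 at 60 h, 1400 at 12 h | not eligible | not eligible | no deviation |
| C | 1400 at 72 h, 900 at 12 h | eligible | eligible | no deviation |
| D | 900 at 168 h only | not eligible | eligible as worded | no deviation |

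A is the conflict within the protocol. B shows the SAP gap: both protocol rules refuse entry, yet the check reports nothing. B gives the same result without the 60 h value, so one early screening sample and one baseline sample are enough to produce it. D shows that the protocol rules can also conflict in the other direction. It is less likely, because Table 2.-1 calls for baseline labs within 48 h of dosing and D requires that count to be missing.

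**Step 3. Illustration of size (assumed inputs, none from the documents)**

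Take one patient with true ALC 1300, within-person SD 0.3 on the log scale, and independent values.

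- One value at or below 1100: Φ(ln(1100/1300)/0.3) = Φ(−0.557) = 0.289.
- Any of two values: 1 − 0.711² = 0.494.
- Any of four values: 1 − 0.711⁴ = 0.744.

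The latest-value rule therefore admits this patient 29% of the time. The any-value rule admits 29% with one in-window sample (no difference), 49% with two and 74% with four. Positive correlation between values would bring the last two figures closer to 29%.

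**The case against.** The strongest reply is that 2d is specific and 6.4.1 is general. Criterion 2d states its own value rule and window, while 6.4.1 is permissive wording meant to help find qualified participants. A site that lets 2d govern is following the only text written for ALC. That reading is reasonable, but the documents do not state it, and the reason 6.4.1 gives for using the latest value points the other way.

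On the SAP, two points stand. The check reports deviations and does not decide who enters, so it is not a third eligibility rule. And requiring every value to fail is the exact complement of 2d's any-value logic, so the two differ only in the window. It can also be argued that the criterion named in SAP 7.2 brings the 96 hours with it and that Appendix 1 is shorthand, since its organ-dysfunction line also drops a time condition. But Appendix 1 is the list identified as programmable, and a programmer working from it would not apply the window.

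The sampling schedule also limits the size. Table 2.-1 plans one screening and one baseline lab, and one sample within 48 hours of dosing can serve as both. Retests are permitted, however, and Protocol Section 9 lets routine counts taken before consent be used, so several values in an ICU patient are plausible.

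A reader might infer that the any-value rule worsens regression to the mean in the ALC endpoint. The documents do not support this. If baseline is the last pre-dose value (an assumption, since the SAP leaves such derivations to internal documents), the direction reverses. On the Step 3 inputs with four samples, the expected shortfall of baseline below the true value is 0.3 × 0.342/0.289 = 0.355 log units under the latest-value rule. Under the any-value rule it is 0.3 × 0.342 × 0.711³/0.744, about 0.05. Here 0.342 is the normal density at 0.557.

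**Conclusion.** The point holds as two textual faults. Criterion 2d and Section 6.4.1 give opposite entry decisions for a recovered ALC, and the SAP check as worded misses a breach of 2d's window. Both follow from the wording and need no numerical assumption. How often either would occur cannot be derived from the documents; the 29%, 49% and 74% are illustrations for one assumed patient, not estimates for this trial.

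The consequence is limited to consistency of enrolment, the count of relevant protocol deviations and the description of the enrolled population. Three stronger inferences are not supported:

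- **That the analysis populations are undefined.** The sets in Protocol Section 10.2 and SAP Section 6.3 do not require a qualifying ALC, so the safety and PK analysis sets are unaffected.
- **That ALC alone keeps out the pro-inflammatory phase.** Protocol Section 3.3 also relies on onset of organ dysfunction at least 24 hours before dosing.
- **That the ban on waivers prevents a resolution.** Clarifying which sentence governs is not a waiver.

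**What to change.** Reconcile the protocol passages. The sponsor decides which rule applies. Section 6.4.1 should then say whether it covers criterion 2d, and both passages should use one time anchor, randomization or dosing.

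Then align the SAP. The ALC check in Section 7.2 and Appendix 1 should use the same value rule and window as the reconciled criterion. Add a listing of the qualifying ALC, its date and time, and the last pre-dose ALC, so that a reader can see who entered on a value that had since recovered.

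The cost is about one sentence in each document, one programmed condition and one listing. Baseline ALC is already summarized and laboratory values are already listed by subject, so no new data collection is needed.
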